NCT04111068

Official Title: Improving Vision in Adults With Macular Degeneration, Study 1: the Effect of Brain Stimulation

Date Last Updated: February 4, 2022

Statistics Analysis Plan

Planned Study Components

- A. Independent Variables:
 - 1. Stimulation Type (active vs sham)
 - 2. Test Time (effect during, effect 5 mins post, effect 30 mins post)
 - For statistical testing, Test time will contain 3 levels, defined as:
 - i. During stimulation baseline
 - ii. 5 mins post stimulation baseline
 - iii. 30 mins post stimulation baseline
- B. Experimental Design and Outcome Measures:
 - 1. 2 (Stim type) x 3 (Test time) analysis: Outcome is Crowded VA in logMAR (FrACT)
 - 2. 2 (Stim type) x 3 (Test time) analysis: Outcome is Uncrowded VA in logMAR (FrACT)
 - 3. 2 (Stim type) x 3 (Test time) analysis: Outcome is RSVP reading analysis
- C. *Interactions:* An interaction between stim type and test time indicates that active stimulation was effective, but not at every timepoint. Therefore, the planned contrast in the event of an interaction:
 - 1. Active vs. sham: individually compare active vs sham at the three timepoints.
- D. Covariates to examine:
 - 1. Language, primary analysis (dichotomous)
 - 2. Age (continuous)
 - 3. Distance visual acuity (will be dichotomized)^a
 - 4. RSVP critical print size (will be dichotomized)^a
 - 5. RSVP maximum reading speed (will be dichotomized) ^a
 - 6. Cognitive Screening: MoCA-blind (UW) and (HKPU) (will be dichotomized) ^b
 - 7. Type of AMD: wet, dry (dichotomous) ^c
 - a. Because the different languages likely elicit different mean performances, covariates listed will be dichotomized with a median split separately for each language to allow combined data analysis with the included covariate. The "low" group will include any participants scoring the median. The "high" group will include only participants scoring better than the median.
 - b. Cognitive Screening will be dichotomized separately for each language along standard thresholds for clinical significance. This covariate will only be tested if at least 5 total participants are allocated to both groups.
 - c. Type of AMD will only be tested if at least 5 total participants are allocated both groups.
- E. Additional Details:
 - 1. The analysis will be run individually for each planned outcome measure.
 - 2. Participants with incomplete data will be excluded from the analysis
 - 3. All tests will be 2-tailed with alpha = 0.05

Analysis Procedure

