- 1. Normality check: Check if ANOVA assumptions are violated (languages combined)
 - 1. Sphericity of variances use Mauchly's Test of Sphericity to check for significant violations of sphericity.
 - Normality of Residuals visually inspect pp plot and qq residual plots evaluate the degree of violation.
 - If sphericity assumption is violated: Use Greenhouse Giesser correction for all main effects and interactions, following *Parametric Statistics*, section 2a
 - If interaction between independent variables is significant: Use Wilcoxonsigned-rank tests for planned pairwise comparisons instead of ttests.
 - If normality assumption is violated: follow *Nonparametric Statistics*, section 2b.

2a. Parametric Statistics

- 1. Primary Analysis:
 - i. Perform repeated-measures ANCOVA, with Language as covariate.
 - If interaction between stimulation type and test time is significant:
 - ii. Examine planned comparisons with within-subject ttests

If language covariate is significant or significantly interacts with another factor:

iii. Run separate repeated-measures ANOVAs for each language

If either ANOVA reveals an interaction:

- iv. Examine planned pairwise comparisons with within-subject ttests
- 2. Secondary Analysis:
 - i. Perform repeated-measures ANCOVA, iteratively with each secondary covariate to be tested.

If interaction between stimulation type and test time is significant:

ii. Examine planned comparisons with within-subject ttests

If any dichotomous covariate is significant or significantly interacts with another factor: iii. Run separate repeated-measures ANOVAs for each level of the covariate

If either ANOVA reveals an interaction:

iv. Examine planned pairwise comparisons with within-subject ttests

2b. Nonparametric Statistics

- 1. Primary Analysis:
 - i. Perform aligned rank transform for nonparametric ANOVA with 3 independent factors.
 - 2 (Stim type) x 3 (test time) x 2 (language) mixed effects ANOVA

If stim type and test time interact, but language is not significant and no interaction involving language occurs:

ii. Run planned pairwise comparisons using Wilcoxon-signed-rank tests

If language is significant or if language significantly interacts with any other factor:

iii. Discard previous analysis and run two separate ART-transformed 2 (stim type) x 3 (test time) nonparametric ANOVAs, one for each level of language.

If either ANOVA reveals an interaction:

iv. Run planned pairwise comparisons with Wilcoxon-signed-rank tests

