2. Secondary Analysis:

i. Perform the same procedure as the primary analysis iteratively for each covariate to be tested.

Aligned-rank transform reference:

Wobbrock et al. (2011). The aligned rank transform for nonparametric factorial analyses using only ANOVA procedures. Proceedings of the SIGCHI conference on human factors in computing systems. https://dl.acm.org/doi/10.1145/1978942.1978963

Data and demographics summary table:

- 1. A summary table will be generated, one row per participant. Columns will include:
 - Age
 - Sex
 - macular degeneration type (wet AMD, dry AMD, JMD
 - language
 - distance VA
 - MNREAD CPS (equivalent to near VA)
 - MNREAD speed
 - RSVP CPS
 - RSVP speed

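### Any significant language term switches the primary active–sham analysis to two per-language analyses, with no alpha control or success rule, and 2a leaves the combined result's status undefined

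*SAP*

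**What the plan says.** For each outcome, the parametric Primary Analysis (SAP, Analysis Procedure 2a.1) opens with a combined model: "Perform repeated-measures ANCOVA, with Language as covariate". The next condition reads "If language covariate is significant or significantly interacts with another factor", and the action is "Run separate repeated-measures ANOVAs for each language". Nothing in 2a says whether the combined result is then kept, replaced or demoted.

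The nonparametric branch (2b.1.iii) has an equivalent trigger but a firmer action: "Discard previous analysis and run two separate ART-transformed 2 (stim type) x 3 (test time) nonparametric ANOVAs, one for each level of language".

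The only statement on error control is in Planned Study Components, E.3: "All tests will be 2-tailed with alpha = 0.05".

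The same device is repeated for the secondary covariates. In 2a.2.iii it is "Run separate repeated-measures ANOVAs for each level of the covariate"; in 2b.2.i it is "Perform the same procedure as the primary analysis iteratively for each covariate to be tested".

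**The concern.** A screen applied to the trial data chooses which result answers the main question, and the SAP does not define success after that choice. There are three gaps.

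- **The trigger is too wide.** A language main effect, or a language-by-time interaction, means that the languages differ in level or in time course. Neither is evidence that active and sham differ by a different amount in the two languages, yet either one displaces or competes with a valid combined test.
- **There is no decision rule after the split.** Two tests at 0.05 replace one, and neither branch says whether a positive result is needed in one language or in both. The SAP's mention of either ANOVA showing an interaction governs follow-up contrasts only.
- **2a and 2b differ.** Two analysts following 2a could report different primary results. The choice between 2a and 2b itself rests on a visual judgement of residual plots, so that judgement also decides whether the combined result survives.

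At stake are the type I error and power of the active–sham conclusion. Less depends on the secondary-covariate splits, because those analyses are labelled secondary.

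**Working it through.** **Plan's own figures.** The documents give alpha = 0.05 two-sided and no sample size, power, effect size or SD. There is no design figure to reproduce.

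**Triggers.** In the 2 (stimulation) × 3 (time) × 2 (language) layout, four terms contain language:

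| Term | Contains stimulation? |
|---|---|
| language | no |
| language × time | no |
| language × stimulation | yes |
| language × stimulation × time | yes |

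With no true effects, and treating the four tests as independent, the chance of a split is 1 − 0.95^4 = 0.185.

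**2a against 2b.** In 2b.1.ii, combined contrasts are run only if no language term is significant. In 2a.1.ii they depend only on stimulation × time, so combined and per-language results can both stand.

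**Error once split, by hand.** The language groups are disjoint. If the split is caused by a language difference unrelated to stimulation, the chance of at least one false positive is 1 − 0.95² = 0.0975. If the main effect and the stimulation × time interaction are both read in each language, treated as independent, it is 1 − 0.95^4 = 0.185.

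**Whole procedure, by simulation.** Assumptions not in the documents:
- change-score outcomes and equal language groups;
- total n of 20, 30 or 40;
- subject SD 0.5, session SD 0.7, residual SD 0.7, so the SD of a subject mean is √(0.25 + 0.49/2 + 0.49/6) = 0.759;
- success judged on the stimulation main effect.

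Each setting had 40,000 runs (Monte Carlo SE about 0.14 points at 8%). Language differences of 0.35 and 0.70 are 0.35/0.759 = 0.46 SD and 0.70/0.759 = 0.92 SD. Type I error in %, for n = 20/30/40:

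| Language difference | Split occurs | Either language, combined discarded | Either language, combined also kept |
|---|---|---|---|
| none | 18.4/18.4/18.8 | 8.3/7.9/8.3 | 8.6/8.1/8.7 |
| 0.46 SD | 28.2/33.8/38.9 | 8.2/8.7/8.9 | not tabulated |
| 0.92 SD | 57.0/73.3/83.7 | 9.0/9.2/9.2 | 10.0/10.5/10.5 |

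With no language difference:
- The combined test alone gives 5.2/4.9/5.2%.
- Splitting only on the two stimulation-containing terms gives 8.1/7.7/8.2%; splitting only on the other two gives 5.6/5.3/5.6%. Nearly all the inflation here comes from chance stimulation-by-language interactions, which select data in which one language looks extreme.
- Requiring both languages gives 4.2/3.9/4.3%.
- Language groups of 6/20, 10/30 and 13/40 give 7.4/7.7/8.0% under the either-language rule.
- The aligned-rank branch (10,000 runs, normal and exponential errors) gives 7.5–8.6% under the either-language rule, against 4.5–5.2% combined. At 0.92 SD the either-language figure is 8.6–10.0%.

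**Power, for an effect giving 80% in the combined test.**
- Either language, combined discarded: 78–79% at 0.46 SD and 75–76% at 0.92 SD.
- Combined also kept, at 0.92 SD: 82–83%, bought with the 10.0–10.5% error above.
- Both languages, within trials that split: 18.7/19.1/19.8% with no language difference, 21.2/22.8/23.4% at 0.92 SD.

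A hand check agrees in scale. With 8 to 20 participants per language, one language alone has power 0.448 to 0.487. Both positive is then 0.448² = 0.20 to 0.487² = 0.24; at least one is 1 − 0.552² = 0.70 to 1 − 0.513² = 0.74.

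**Sensitivity to the assumptions.** A simpler model used 8 to 20 participants per language, active–sham correlation 0.5, and only the language and language × stimulation triggers. Either-language error was 7.8% with no shift, 8.8–9.4% with a 1 SD shift and 9.5–9.8% with a 2 SD shift.

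**The case against.** The strongest reply is that the inflation depends on rules the SAP never states: a single trial-level claim, either language sufficing, and the stimulation main effect as the test of success. If each language is reported as its own claim, no either-language claim arises; if both must be positive, error is not inflated. This stands as a limit on the numbers, which are conditional. It does not answer the point that the rule is missing.

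Second, the triggers without a stimulation term add little when the languages do not differ (5.3–5.6% against 4.9–5.2%). That is correct. They matter when the languages do differ, by making splits common and costing power.

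Third, the 0.92 SD case has weak support. The SAP's remark about languages differing in mean performance concerns covariates to be median-split. The protocol sets each participant's RSVP condition to a common 55% target, and the other two outcomes are Landolt C acuities that involve no reading. The case is best read as a stress test, but error of about 8% appears with no language difference at all.

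Fourth, 2a read literally keeps both results, since no step removes the combined one. That is a fair reading, but it gives the highest error of the rules simulated and still does not say which result carries the conclusion.

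Finally, the split is prespecified, and reading English and reading Chinese characters are different tasks, so per-language results are reasonable to show. They can be shown without letting a significance test promote them.

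**Conclusion.** The concern holds and should be fixed. The missing success rule, the absence of alpha control across languages, and the difference between 2a and 2b follow from the text alone. Each trial-level success rule simulated does worse than the combined test on error or on power. Counting either language raises type I error from about 5% to about 8% with no language difference and about 9% at 0.92 SD, or 10.0–10.5% there if the combined result is also kept. Requiring both languages leaves power of 19–23% in trials that split.

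The 9.75% figure needs only the SAP's alpha and two disjoint groups. The simulated figures rest on assumed sample sizes, SDs, change-score outcomes, language shares and language differences, and on taking the stimulation main effect as the test of success. Repeat runs of the parametric equal-group settings agree within a few tenths of a point on error and one to three points on power; the aligned-rank and unequal-group settings were not repeated.

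**What to change.** State in both 2a and 2b that the combined-language model, with language as a between-subject factor, is the primary result whatever the language p-values. Delete the instruction in 2b.1.iii to discard the combined analysis. Report the stimulation-by-language term with a confidence interval, and the per-language active–sham estimates with confidence intervals, as supportive only. Treat splits on the secondary covariates the same way.

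Two narrower repairs are weaker. Splitting only on language × stimulation still gives 7.7–8.0% error under the either-language rule. An either-language rule with 0.025 per language gives 1 − 0.975² = 0.049 once split for reasons unrelated to stimulation, but about 6.5% overall with no language shift in the simpler model, because a stimulation-by-language interaction can itself cause the split. If the sponsor wants a confirmatory split, the SAP must state the alpha allocation and whether one language or both must be positive, and must deal with that residual inflation.

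The cost is SAP wording only. The downside is that if stimulation works in one language only, the combined effect is an average; the per-language estimates would show this.

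### Subgroup ANOVAs triggered by the covariate models re-test stimulation at 0.05 and may support a stimulation claim: with no true effect, the chance of a significant result in one outcome rises from about 10% to about 40–44%

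*SAP*

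**What the plan says.** - SAP, Additional Details: "The analysis will be run individually for each planned outcome measure", and "All tests will be 2-tailed with alpha = 0.05". The outcomes are crowded acuity, uncrowded acuity and RSVP reading. The SAP does not rank them. The protocol's treatment-day steps put RSVP under primary outcomes and the Landolt C tests under secondary outcomes.
- SAP 2a, Primary Analysis: "Perform repeated-measures ANCOVA, with Language as covariate".
- SAP 2a, Secondary Analysis: a new ANCOVA, "iteratively with each secondary covariate to be tested". The candidates are age, distance acuity, RSVP critical print size, RSVP maximum speed, MoCA and AMD type.
- Two of these six are conditional. For MoCA: "This covariate will only be tested if at least 5 total participants are allocated to both groups". For AMD type: "Type of AMD will only be tested if at least 5 total participants are allocated both groups".
- In each secondary model a significant stimulation-by-time term opens the active-versus-sham comparisons. If a dichotomous covariate is significant, or interacts with any factor, the instruction is "Run separate repeated-measures ANOVAs for each level of the covariate", followed by more pairwise tests.
- The Interactions item of the SAP reads a stimulation-by-time interaction as evidence that active stimulation worked at some time points.
- Section 2b repeats the loop with aligned-rank ANOVAs.
- Neither document gives a multiplicity rule, an exploratory label for these tests, or a sample size.

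**The concern.** The secondary models do more than look for effect modifiers, because each one tests again whether stimulation works. The split rule is also loose. A covariate main effect compares kinds of patient averaged over active and sham sessions, yet it is enough to order two new stimulation analyses in smaller groups. Since the SAP treats a stimulation-by-time result as a sign of efficacy and does not confine that reading to the primary model, a statement that brain stimulation affects reading or acuity could rest on one subgroup ANOVA out of many. What needs to be known is how often that happens by chance, and which part of the procedure causes it.

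**Working it through.** The plan states no family-wise error rate, so there is no figure to reproduce beyond the per-test 0.05.

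**Inputs from the documents**
- Three outcomes, each with the full procedure.
- Up to seven models per outcome: Language plus six secondary. Five are certain (Language, age, distance acuity, print size, speed).
- Six dichotomous covariates at most, four of them certain. Age is continuous and triggers no split.
- Two stimulation tests per model: main effect and stimulation-by-time.
- Four trigger tests per dichotomous covariate: covariate, covariate-by-time, covariate-by-stimulation, and the three-way term.

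**Assumptions, not in the documents**
- n = 20, 30 or 50.
- Correlation 0.5–0.7 between time points, 0–0.9 between outcomes, 0–0.5 between covariates.
- Covariates mean-centred; sphericity and normality hold.

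**Hand check, treating tests as independent**
1. Primary model, two tests: 1 − 0.95² = 9.8%.
2. One covariate triggers a split by chance: 1 − 0.95⁴ = 18.5%.
3. A split gives two levels with two tests each, again 18.5%. Trigger and hit together: 0.185 × 0.185 = 3.4%. Over six covariates: 1 − (1 − 0.034)⁶ ≈ 19%.
4. With about 12% from the pooled models: 1 − 0.88 × 0.81 ≈ 29%.

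Step 3 is too low, because trigger and hit are not independent. With equal halves, the stimulation effect in one half and the difference between the halves correlate at 1/√2 = 0.71. A chance covariate-by-stimulation term therefore makes a subgroup stimulation result more likely.

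**Simulation of section 2a with no stimulation effect** (6,000 trials per scenario). A hit is a significant stimulation main effect or stimulation-by-time term, in either direction.

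| Tests counted | One outcome | Any of three |
|---|---|---|
| Language model only | about 10% | 16–26% |
| All seven pooled models | 11–13% | 19–32% |
| Five certain models plus triggered splits | about 33% (32–37%) | 50–73% |
| All seven models plus triggered splits | 40–44% | 60–81% |

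The low end of the last two entries for any of three outcomes is at outcome correlation 0.9. Each dichotomous covariate triggered a split in about 18% of trials when nothing but chance was at work, which agrees with step 2. Going from one pooled model to seven adds 1–3 percentage points; the splits add most of the rest.

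**Sensitivity**
- Main effects only, full loop: 23–26% for one outcome.
- An interaction counted only if a follow-up t-test is also significant: 55–70% across three outcomes, 49% at outcome correlation 0.9.
- Covariates not centred (the SAP does not say), n = 30: 55% for one outcome and 90% for any of three.
- Only results favouring active, in a separate simulation of one outcome (n = 20 and 30, 2,000 trials each, independent covariates): 3–5% from the primary model, 14% with the five certain models and their splits, 19–20% with all seven.

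**The case against.** The strongest reply is that the plan already has a hierarchy. Language is marked as the primary analysis, every other covariate sits under a secondary heading, and the protocol names RSVP as primary. A reader might infer that nothing at all limits which result counts; the documents do not support that. What remains is that the labels are not made binding. The secondary section orders the same contrasts at the same level, and the protocol's ranking of outcomes is not carried into the SAP.

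A reader might also blame the number of models. The pooled models are nearly redundant when covariates are centred, because they re-test almost the same contrast on the same patients. Two of the seven may never be run. That part of the reply stands.

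A third tempting reading is that a false claim of benefit is more likely than not. The high figures count results favouring sham and pool all three outcomes. For benefit alone the figure is 14–20% per outcome. Even if the three outcomes were independent, it would be 1 − 0.86³ = 36% to 1 − 0.80³ = 49%. That is well above nominal, but the working does not show a false claim of benefit to be likely.

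In section 2b, a Language-triggered split replaces the pooled result. Dropping pooled results in this way left the simulated rates unchanged with centred covariates. The aligned-rank tests themselves were not simulated.

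**Conclusion.** The concern holds, with the triggered splits as its main cause. With no stimulation effect, the chance of a significant stimulation or stimulation-by-time result in one outcome is about 10% from the primary model, 11–13% from all pooled models and about 40–44% with triggered splits (about 33% if only the certain dichotomous covariates are used). Across three outcomes it is about 60–81%, depending on their correlation. The exact values rest on assumed sample sizes and correlations, centred covariates and two-sided counting. They change little from n = 20 to n = 50, and the full procedure exceeded 5% in every scenario tried. The SAP should be changed on this point; the primary analysis itself need not be redesigned.

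**What to change.** 1. State that conclusions about stimulation and stimulation-by-time come only from the primary Language model, with RSVP as the primary outcome, as in the protocol, and the two Landolt C outcomes as secondary.
2. Do not split on a covariate main effect or a covariate-by-time term, for Language as well as the secondary covariates. Split only on a covariate-by-stimulation or covariate-by-stimulation-by-time term.
3. In the secondary models interpret only those two kinds of term, Holm-adjusted over all that are tested. Report them and any subgroup results as exploratory effect-modifier analyses that cannot support an efficacy claim.
4. Apply the same rules in section 2b.

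Item 2 is not enough alone, because a chance covariate-by-stimulation term still opens subgroup tests that tend to be significant. Items 1 and 3 are what control the error rate.

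The Language model still has two stimulation tests, about 10% per outcome at 0.05 each. If 5% is intended, test each at 0.025; in 20,000 null trials per scenario this gave 5.0–5.2% for RSVP.

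The change is to SAP wording only, with no new data or visits. The cost is that secondary covariate findings become harder to call significant.
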